11.2 Adverse Events

Verbatim adverse event terms reported by investigator will be coded to the preferred term (PT) level using the Medical Dictionary for Regulatory Affairs (MedDRA) dictionary. SAS datasets containing Standard MedDRA Queries (SMQs) will be generated directly from the MedDRA dictionary and merged with investigator-reported data by preferred term to identify occurrences of specified groupings of adverse events.

The planned periods of observation, starting with the time of written informed consent, for collecting AEs in this study are described below:

- All AEs through Visit 8/Day 90, regardless of relationship to the investigational product
- AEs related to the investigational product through the end of study
- AEs leading to discontinuation and AEs leading to withdrawal of consent through the end of the study
- All SAEs will be collected through the end of the study, regardless of relationship to investigational product

All adverse and clinical (suspected MACE) events will be entered on the AE / SAE eCRF form utilizing an appropriate event category. In order to distinguish between clinical events (which are adjudicated, and analyzed/reported as efficacy endpoints) and adverse events occurring during the study, an AE flag variable will be derived as described below. All adverse events where the flag is set to Yes will be included in the estimation of AE incidence rates.

Set AE Flag=No if:

- AE outcome = fatal and adjudicated as CVD or undetermined cause of death
- AE outcome non fatal, reported by site as a CV endpoint, adjudication by the CEC as meeting CV endpoint criteria
- AE outcome non fatal, reported by site as an AE, triggered adjudication by the CEC as meeting CV endpoint criteria

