10.1 Analysis of Primary Endpoint

The primary endpoint is defined as the time to first occurrence of any component of the composite MACE, ie, CV death, MI, or stroke, from the time of randomization through 90 days. This analysis will be based on events adjudicated and confirmed by the CEC. All adjudicated MIs from randomization through 90 days will be included in the analysis of the primary endpoint. A total of 1004 events for the primary composite endpoint are targeted as per the power calculation. However, the final analysis will include all events that are observed during the 90-day interval even if that number is larger or smaller than the target.

For each subject, time to event is defined as the time (number of days) from randomization to the first occurrence of confirmed CV death, MI, or stroke during 90 days of follow-up. For subjects without an event and last MACE ascertainment date occurring at least 90 days after randomization, an administrative censoring will be applied at 90 days. For subjects that experience a non-CV death prior to 90 days of follow-up, censoring will occur on the date of death. All other subjects will be censored on the last MACE ascertainment study day. The analysis of the primary endpoint will be based on positively adjudicated, CEC confirmed events occurring in the 90 days following randomization.

The estimand [ICH E9 (R1)], ie, the quantity to be estimated, in the primary analysis is defined as the hazard ratio for CSL112 vs. placebo, regardless of non-initiation, missed dose or discontinuation of treatment, in addition to standard of care as taken, for time to first occurrence of CV death, MI or stroke through 90 days in subjects with ACS presenting with STEMI or NSTEMI and MVD, while subjects have not died due to non-CV causes.

The following algorithm will be applied to derive two analysis variables, one corresponding to time in days and a second corresponding to censoring status. Any death with cause adjudicated as “undetermined” will be included as CV death in the primary analysis. The table below gives the derivation algorithm to be used in the primary analysis.

	Time to Event (days) [TTE]	Censoring Status [Censor]
First of confirmed CV death, MI, or Stroke during 90 days following randomization	(date of MACE – randomization date) + 1	0
Last MACE ascertainment on or after 90 days of follow-up without experiencing MACE	90	1

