11.2.1 Treatment-emergent Adverse Events

Treatment-emergent AEs (TEAEs) are defined as AEs occurring on or after the start date of the first infusion. AE severity is determined on a scale from mild, moderate to severe.

An overview summary of all TEAEs will be summarized as described below. The number (%) of subjects experiencing events in each category will be displayed by treatment group.:

- Any TEAE through day 90 / through end of study
- TEAEs that begin within 24 hours of start of an investigational product infusion
- TEAEs that begin after 24 hours from the start of investigational product infusion and are related to study treatment
- TEAEs that are related to investigational product, irrespective of start time
- Non-fatal TEAEs leading to permanent discontinuation of investigational product (ie, TEAEs that cause permanent cessation of all further study treatment)
- Non-fatal TEAEs leading to withdrawal from study
- TEAEs leading to dose interruptions (ie, TEAEs which occur during an infusion and cause that infusion to be temporarily or permanently halted)
- TEAEs leading to skipped infusions (ie, TEAEs which do not resolve in time to allow all 4 infusions to be administered within 30 days)
- SAEs
- SAEs related to study treatment
- Fatal SAEs
- Fatal SAEs related to study treatment
- TEAEs of special interest including drug hypersensitivity, acute kidney injury, potential hepatic injury, and new onset or worsening of heart failure

Non-TEAEs will be included in a data listing but not in a summary table.

The following summaries of TEAEs will be presented and will display the number of subjects and the number of events. With the exception of summary tables by worst severity (described further below), subjects with multiple occurrences of the same TEAE will be counted once; however, all occurrences of the TEAE will be reflected in the event count. In the summary tables by worst severity, subjects will be counted once in the most severe category at overall, SoC, and each unique PT level. Multiple occurrences of the same PT with the same severity are all counted at overall, SoC, and PT levels; however, multiple occurrences of the same PT with different severities are counted in the most severe category at overall, SoC and PT levels. The frequency and percentage of TEAEs will be summarized and displayed in two

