11.2.4 Deaths

CEC-adjudicated deaths will be summarized by displaying the number and percentage of subjects within categories of CV and non-CV death. All deaths adjudicated with an undetermined cause of death will be analyzed as CV death. Deaths among screen failed subjects will be listed separately.

11.2.5 Adverse Events Leading to Discontinuation of Study Treatment, Withdrawal from the Study, and Other Significant Adverse Events

The following categories of treatment-emergent AEs will be summarized:

- Treatment-Emergent AEs Leading to Discontinuation of Study Treatment
- Treatment-Emergent AEs leading to Withdrawal from the Study
- Treatment-Emergent AEs Leading to Infusion Interruptions

The following listings will be provided:

- Treatment-Emergent AEs Leading to Discontinuation of Study Treatment
- Treatment-Emergent AEs leading to Withdrawal from the Study
- Treatment-Emergent AEs Leading to Infusion Interruptions

11.3 Adverse Events Meeting Pre-specified Criteria:

Adverse events meeting at least one of the following criteria, as specified by the FDA, in communication with CSL, for identification of potential adverse drug reactions, will be reported by SoC and PT. A separate tabular summary will be generated for each of the four bullets below as well as a combined summary of all AEs meeting the pre-specified criteria:

1. AEs that begin within 24 hours after the start of an infusion
2. AEs that begin more than 24 hours after the start of infusion and reported as at least possibly causally related to the administration of study treatment by the investigator or sponsor. It is noted however that the reference to sponsor assessment of causality is part of the FDA definition but this information is not captured in the clinical database.
3. AEs for which the investigator's causality assessment is missing or indeterminate

4. Exposure adjusted incidence of TEAEs: all AEs, for which the incidence in an active treatment arm exceeds the exposure-adjusted incidence rate in the placebo arm by 30% or more on a relative basis, provided the difference in incidence rates is 1% or more. The algorithm is shown below:

For each PT recorded on the AE page of the eCRF, the following algorithm will be applied to define whether or not the PT in question meets the criterion defined in bullet 4.

$$\text{Incidence Rate (IR)} = \frac{\text{Total Number of Subjects with TEAEs}}{\text{Total Number of Subjects}}$$

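### The SAP's AE flag takes fatal adverse events with an undetermined cause of death out of the AE incidence tables, so their reported term and causality are not compared by arm

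*SAP*

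**What the plan says.** SAP 11.2 has sites enter both adverse events and suspected MACE on one form, then derives a flag to separate them. The stated purpose is "In order to distinguish between clinical events (which are adjudicated, and analyzed/reported as efficacy endpoints) and adverse events occurring during the study". The scope is given as "All adverse events where the flag is set to Yes will be included in the estimation of AE incidence rates".

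Three rules set the flag to No:

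- Fatal: "AE outcome = fatal and adjudicated as CVD or undetermined cause of death".
- Non-fatal, reported as an endpoint: "AE outcome non fatal, reported by site as a CV endpoint, adjudication by the CEC as meeting CV endpoint criteria".
- Non-fatal, reported as an AE: removed if a triggered CEC adjudication finds that it meets CV endpoint criteria.

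The planned outputs in SAP 11.2.1 include a row for "Fatal SAEs related to study treatment", and SAP 11.2.3 plans tables of fatal and related fatal SAEs. For deaths, SAP 11.2.4 says "CEC-adjudicated deaths will be summarized by displaying the number and percentage of subjects within categories of CV and non-CV death", and adds that "All deaths adjudicated with an undetermined cause of death will be analyzed as CV death". In efficacy, SAP 10.1 says that a death of undetermined cause "will be included as CV death in the primary analysis".

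**The concern.** The two non-fatal rules ask whether the event itself met CV endpoint criteria. The fatal rule asks only how the death was classified. Where the CEC establishes a CV cause, removal fits the flag's purpose. Where the CEC cannot determine a cause, no CV event has been established. The death counts as CV by a convention adopted for efficacy, and the flag carries that convention into safety, where it works in the less cautious direction.

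At stake is the visibility of fatal events that might be drug reactions. Hypersensitivity matters most. The protocol (1.4 and 7.1) names it as a potential risk for both CSL112 and the albumin placebo, and it is the only one of the four special-interest categories whose main analysis is built from AE preferred terms. In tables of rare fatal events, a few records in one arm can change the reading.

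**Working it through.** No arithmetic applies. The documents attach no count or rate to this rule, so the check is to follow one record through the planned outputs.

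**Hypothetical record.** The site reports anaphylaxis, outcome fatal, related, with onset within 24 hours of an infusion. The CEC adjudicates the cause of death as undetermined.

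**Step 1, the flag.** The outcome is fatal and the adjudicated cause is undetermined, so the flag is No. The preferred term and causality are not inputs to the rule. Neither non-fatal rule applies.

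**Step 2, each output.** I take the flag to apply wherever subjects or events with AEs are counted, since no section states an exemption.

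| Output | Built from | Record counted? |
|---|---|---|
| TEAE and SAE tables, fatal SAEs, related fatal SAEs (11.2.1, 11.2.3) | AE records | No |
| Criteria for potential adverse drug reactions (11.3) | AE records | No |
| Hypersensitivity tables (11.2.2) | AE terms in the SMQ | No |
| Supporting kidney and hepatic SMQ tables (11.2.2), for a fatal event with such a term | AE terms in the SMQ | No |
| Main kidney injury and potential hepatic injury counts (11.2.2) | Central laboratory values | Flag not used |
| Adjudicated liver injury; new or worsening heart failure (11.2.2) | CEC adjudication | Flag not used |
| Deaths table (11.2.4) | CEC adjudication | Yes, as CV death, without term or causality |
| Primary endpoint (10.1, if within 90 days) and mortality analyses (10.3, 10.4) | Adjudicated deaths | Yes, without term or causality |
| All-AE and fatal SAE listings (11.2.1, 11.2.3) | AE records | No flag restriction stated; not a by-arm comparison |

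**Step 3, missing causality.** SAP 8.1.2 treats a missing causality assessment as related. That safeguard has no effect in these tables on a record already flagged No.

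**Step 4, the protocol.** Protocol 9.1.3 requires that the event be the cause of death for the fatal seriousness criterion to be met. A fatal record is therefore the investigator's statement about why the subject died. Protocol 9.6.4 exempts suspected MACE from expedited reporting; it does not address aggregate tables. Protocol 9.6.5 turns a suspected CV death into an SAE only when the CEC finds a non-CV cause, and does not mention undetermined deaths. Protocol 2.2.4.2 and 10.3.3.2 plan SAE and AE summaries with no such exclusion.

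**Step 5, COVID-19.** SAP 7.1 places every COVID-19 associated adverse event in the standard AE tables and plans a row for fatal COVID-19 TEAEs. SAP 11.2 removes a fatal COVID-19 event if the death is adjudicated CV or undetermined. For such a record the two statements cannot both be followed.

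**The case against.** The strongest defence is that the flag does what it was built to do. CV and undetermined deaths are both primary-endpoint events under SAP 10.1, and removing adjudicated endpoints from AE tables is its declared purpose. CEC adjudication also overrides the site's report in the third rule. The rule works record by record, so a separate non-fatal kidney or hypersensitivity event in a subject who later dies is kept. The troubling example needs the blinded CEC to disagree with the investigator's fatal term or to find the cause unclear, and how often that happens depends on a charter outside these documents. An excess of deaths would still be seen: SAP 4.6.1.2 has the IDMC test all-cause mortality, with a two-sided 0.01 threshold in favour of placebo.

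Most of this stands, and it limits the point. A reader might infer that special-interest events leave every AE table. They do not, because the main kidney, hepatic and heart failure counts rest on laboratory values or adjudication. A reader might infer that the deaths disappear from safety reporting. They do not, as the deaths table and mortality analyses show. A reader might also take all CV and undetermined deaths in a trial of about 17,400 subjects as the number affected. The documents give neither rate, and such a total would include deaths of determined CV cause, which the flag may properly exclude.

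The defence does not answer the undetermined deaths. Endpoint status there is an analysis convention, and the surviving counts carry no preferred term and no causality.

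**Conclusion.** The point holds in a limited form and is a cheap improvement. As written, the fatal rule removes treatment-related, hypersensitivity and other AE records from the AE-record-based incidence tables when the death is of undetermined cause. No planned by-arm table restores their term and causality. The 11.2.4 table cannot do so, because it merges undetermined with CV deaths. The conflict with SAP 7.1 is a separate inconsistency in the text.

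The size is unknown: the documents give no rate of undetermined deaths and no rate of fatal AEs by term. The conclusion assumes that the flag governs all AE count tables, which follows from the stated scope and the absence of exemptions. No efficacy conclusion is affected.

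**What to change.** - In SAP 11.2, limit the fatal rule to deaths that the CEC adjudicates to a determined CV cause. Keep the flag at Yes for fatal AEs with an undetermined cause of death.
- Add one table of the fatal AEs still flagged No, by arm, preferred term and investigator causality.
- In SAP 11.2.4, show undetermined as its own row.
- In SAP 7.1, state how a fatal COVID-19 event is handled when the flag is No, so that the two sections agree.

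Counting undetermined deaths as CV death in the efficacy analyses stays as it is. The cost is one derivation, one table and a few lines of SAP text, with no new data. The small downside is that some deaths will appear in both efficacy and safety tables, which a footnote can explain.

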11.2.1 Treatment-emergent Adverse Events

Treatment-emergent AEs (TEAEs) are defined as AEs occurring on or after the start date of the first infusion. AE severity is determined on a scale from mild, moderate to severe.

An overview summary of all TEAEs will be summarized as described below. The number (%) of subjects experiencing events in each category will be displayed by treatment group.:

- Any TEAE through day 90 / through end of study
- TEAEs that begin within 24 hours of start of an investigational product infusion
- TEAEs that begin after 24 hours from the start of investigational product infusion and are related to study treatment
- TEAEs that are related to investigational product, irrespective of start time
- Non-fatal TEAEs leading to permanent discontinuation of investigational product (ie, TEAEs that cause permanent cessation of all further study treatment)
- Non-fatal TEAEs leading to withdrawal from study
- TEAEs leading to dose interruptions (ie, TEAEs which occur during an infusion and cause that infusion to be temporarily or permanently halted)
- TEAEs leading to skipped infusions (ie, TEAEs which do not resolve in time to allow all 4 infusions to be administered within 30 days)
- SAEs
- SAEs related to study treatment
- Fatal SAEs
- Fatal SAEs related to study treatment
- TEAEs of special interest including drug hypersensitivity, acute kidney injury, potential hepatic injury, and new onset or worsening of heart failure

Non-TEAEs will be included in a data listing but not in a summary table.

The following summaries of TEAEs will be presented and will display the number of subjects and the number of events. With the exception of summary tables by worst severity (described further below), subjects with multiple occurrences of the same TEAE will be counted once; however, all occurrences of the TEAE will be reflected in the event count. In the summary tables by worst severity, subjects will be counted once in the most severe category at overall, SoC, and each unique PT level. Multiple occurrences of the same PT with the same severity are all counted at overall, SoC, and PT levels; however, multiple occurrences of the same PT with different severities are counted in the most severe category at overall, SoC and PT levels. The frequency and percentage of TEAEs will be summarized and displayed in two

ways: 1) in descending order of incidence in CSL112 arm by System Organ Classes (SOC) and PT and 2) in descending order of incidence in CSL112 arm by PT only. In the SOC row, the number of subjects with multiple events under the same system organ class will be counted once. The following summaries will be provided as described above:

- All Treatment-Emergent Adverse Events through day 90 by SoC and PT
- All Treatment-Emergent Adverse Events through end of study by SoC and PT
- All Treatment-Emergent Adverse Events through day 90 by Worst Severity, SoC and PT
- All Treatment-Emergent Adverse Events through end of study by Worst Severity, SoC and PT
- All Treatment-Emergent Adverse Events through day 90 by PT
- All Treatment-Emergent Adverse Events through end of study by PT
- All Treatment-Emergent study treatment-related Adverse Events, SoC and PT
- Study treatment-related TEAEs with onset after the start of infusion of investigational product. Missing relationship to study treatment will be imputed as described in [Section 8.1.3](#); this summary will also include the number and percentage of TEAEs with a missing relationship to aid in interpretation of the results.

The following listing will be provided:

All Adverse Events - this listing will include treatment, stratification factors, age, sex, race, SoC, PT, verbatim term, Start, End, and duration, severity, serious (yes or no), relationship to treatment (yes or no), outcome, and action taken.

11.2.2 Adverse Events of Special Interest (AESI)

The following TEAEs are considered to be of special interest:

- Hypersensitivity : SMQ narrow 20000214 for Hypersensitivity will be used to identify the relevant preferred terms. The following summary tables will be produced.
 - An overview of adverse events related to hypersensitivity
 - Hypersensitivity by PT
 - Hypersensitivity by PT separately for serious and non-serious AEs

- Treatment-related hypersensitivity by PT
- Treatment-related serious hypersensitivity events by PT
- Acute kidney injury (AKI):
 - This AESI is defined based on central laboratory values. Any increase in serum creatinine value of $\geq 27 \mu\text{mol/L}$ (0.3mg/dL) from the baseline serum creatinine during the Active Treatment period will be considered an AESI.
 - Any increase in serum creatinine value of $\geq 27 \mu\text{mol/L}$ (0.3mg/dL) from the baseline serum creatinine on two consecutive occasions during the Active Treatment period will also be summarized.
 - Relevant preferred terms based on MedDRA SMQ Acute Renal Failure, narrow 20000003 will be summarized to provide additional, supportive analyses of kidney safety/injury and will include the following summaries:
 - An overview of AKI events
 - AKI events by PT
 - Serious AKI events by PT
 - Non-serious AKI events by PT
 - Treatment-related AKI events by PT
 - Treatment-related serious AKI events by PT
- Potential hepatic injury (PHI):
 - This AESI is defined based on central laboratory values. Occurrence of either concomitant elevations of $\text{ALT} > 3 \times \text{ULN}$ with $\text{TBili} > 2 \times \text{ULN}$, or $\text{ALT} > 5 \times \text{ULN}$ at any time during the study will be considered an AESI.
 - Potential drug-induced liver injury (DILI) will be adjudicated by the CEC. Number (%) of subjects with a positively-adjudicated event will be summarized. The CEC adjudication process will include both central and local lab results.
 - A supporting table of AESI as described in the first bullet including both central and local lab results.
 - Supporting summaries of hepatic events by PT where events will be identified using the following MedDRA SMQs:
 - Cholestasis and jaundice of hepatic origin (SMQ) [20000009] – Broad

- Hepatic failure, fibrosis and cirrhosis and other liver damage-related conditions (SMQ) [20000013] – Broad
- Hepatitis, non-infectious (SMQ) [20000010] – Broad
- Liver related investigations, signs and symptoms (SMQ) [20000008] – Broad
- The summary tables of AEs related to PHI will include the following:
 - Overview of PHI events
 - PHI events by PT
 - Serious PHI events by PT
 - Non-serious PHI events by PT
 - Treatment-related PHI events by PT
 - Treatment-related Serious PHI events by PT
- New or worsening heart failure – will be adjudicated by the CEC. The number (%) of subjects positively adjudicated will be reported.

A summary table will be provided to present the number (%) of subjects experiencing each AESI by treatment group along with point and 95% CI [[Newcombe, 1998](#)] estimates for the treatment difference.

Supportive data listings will be produced for each AESI.

